#### **4.14.1. Extent of Exposure**

Duration of exposure (in weeks) to study drug will be summarized for the safety population by treatment group using descriptive statistics. Cumulative exposure and duration of exposure will be summarized in terms of frequency counts and percentages by category and treatment group.

Duration of exposure will be calculated as follows, unless otherwise stated:

- Duration of exposure to investigational product, excluding exposure post treatment change or rescue to baricitinib: *date of last dose of study drug – date of first dose of study drug + 1*.

Last dose of treatment is calculated as last date on the study drug. See the compound level safety standards for more details.

Total patient-years (PY) of exposure will be reported for each treatment group for overall duration of exposure. Descriptive statistics will be provided for patient-weeks of exposure and the frequency of patients falling into different exposure ranges will be summarized. Exposure ranges will generally be reported in weeks using the following as a general guide and may be adjusted based on exposure time at the interim locks and final lock:

- $\geq 4$  weeks,  $\geq 8$  weeks,  $\geq 12$  weeks,  $\geq 16$  weeks,  $\geq 24$  weeks,  $\geq 36$  weeks,  $\geq 52$  weeks,  $\geq 76$  weeks,  $\geq 104$  weeks,  $\geq 120$  weeks,  $\geq 136$  weeks,  $\geq 152$  weeks,  $\geq 168$  weeks,  $\geq 184$  weeks,  $\geq 200$  Weeks and  $\geq 248$  Weeks
- $>0$  to  $<4$  weeks,  $\geq 4$  weeks to  $<8$  weeks,  $\geq 8$  weeks to  $<12$  weeks,  $\geq 12$  to  $<16$  weeks,  $\geq 16$  to  $<24$  weeks,  $\geq 24$  to  $<36$  weeks,  $\geq 36$  to  $<52$  weeks,  $\geq 52$  to  $<76$  weeks,  $\geq 76$  to  $<104$  weeks,  $\geq 104$  to  $<120$  weeks,  $\geq 120$  to  $<136$  weeks,  $\geq 136$  to  $<152$  weeks,  $\geq 152$  to  $<168$  weeks,  $\geq 168$  to  $<184$  weeks,  $\geq 184$  to  $<200$  weeks, and  $\geq 200$  weeks to  $<248$  weeks, and  $\geq 248$  weeks.

Overall exposure will be summarized in total PY which is calculated according to the following formula:

*Exposure in PY (PYE) = sum of duration of exposure in days (for all patients in treatment group) / 365.25.*

#### **4.14.2. Adverse Events**

Adverse events are recorded in the eCRFs. Each AE will be coded to system organ class (SOC) and preferred term (PT) using the Medical Dictionary for Regulatory Activities (MedDRA) version that is current at the time of database lock. Severity of AEs is recorded as mild, moderate, or severe.

A treatment-emergent adverse event (TEAE) is defined as an event that either first occurred or worsened in severity after the first dose of study treatment and on or prior to the last visit date during the analysis period. The analysis period is defined as the treatment period plus up to 30 days off-drug including follow-up time. For the Weeks 0 to 36 TFLs, the analysis period is defined as first dose date up to min(last dose date+30 days, Week 36 visit date, study disposition date). The Week 36 visit date will be imputed if it's missing. Refer to the compound level safety standards for more details including data imputations.

In general, summaries will include the number of patients in the safety population (N), frequency of patients experiencing the event (n), and the relative frequency (that is, percentage;  $n/N \times 100$ ). For any events that are gender-specific based on the displayed PT, the denominator used to compute the percentage will only include patients from the given gender.

Extended Safety Analysis includes patients who were continuously treated with Baricitinib 2-mg, or 4-mg and Placebo from baseline and censored in case of dose change, or after the permanent study drug discontinuation, whichever occurred earlier. In addition to the above treatment groups "ALL BARI" will also be included to the summary which includes patients who received at least one dose (2-mg, or 4-mg) of BARICITINIB at any time of the treatment period.

In an overview table, the number and percentage of patients in the safety population who experienced death, an SAE, any TEAE, discontinuation from the study due to an AE, permanent discontinuation from study drug due to an AE, or a severe TEAE will be summarized by treatment group.

The number and percentage of patients with TEAEs will be summarized by treatment group in 3 formats:

- by MedDRA PT nested within SOC with decreasing frequency in SOC, and events ordered within each SOC by decreasing frequency in the baricitinib 4-mg dose group or other treatment group in the long-term safety analysis as appropriate.
- by MedDRA PT with events ordered by decreasing frequency in the baricitinib 4-mg dose group or other treatment group in the long-term safety analysis as appropriate.

- by maximum severity by treatment using MedDRA PT ordered by decreasing frequency in the baricitinib 4-mg dose group or other treatment group in the long-term safety analysis as appropriate. For each patient and TEAE, the maximum severity for the MedDRA level being displayed is the maximum postbaseline severity observed from all associated lowest level terms (LLTs) mapping to that MedDRA PT.

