a Applicable to all patients at time of screening See EC [9] in protocol for treatments that will require washout.

b The maximal baricitinib dose for patients with renal impairment (defined as eGFR <60 mL/min/1.73 m^2) will be 2-mg QD (see Protocol).

- c At Week 36 patients in the placebo treatment arm who have NOT achieved SALT  $\leq 20$  will be rescued and re-randomized in a 1:1 ratio to baricitinib 2-mg or baricitinib 4-mg. All patients in the baricitinib treatment arms will continue in their current treatment arm regardless of treatment response at Week 36. Patients in the placebo arm who have achieved a SALT  $\leq 20$  will remain on placebo at Week 36. These patients who have experienced spontaneous regrowth on the scalp will remain on placebo for the remainder of the trial, even if relapse is observed later during the study.
- d At Week 52, responders (SALT  $\leq 20$ ) who are eligible (i.e., stayed on the same dose of baricitinib from initial randomization at Visit 2) will be randomized in a 3:1 ratio to either stay on their current dose of baricitinib or transition to placebo (randomized withdrawal).
- e Patients who have been in the baricitinib 4-mg treatment group from Baseline and who have never achieved a SALT  $\leq 20$  by Week 52 AND do not have a  $\geq 2$  point improvement in ClinRO Measure for Eyebrow or Eyelash Hair Loss (nonresponders) at Week 52 will be automatically transitioned to placebo. See footnote “f” for discontinuation criteria at Week 76.
- f Patients who are nonresponders (a SALT  $> 20$ ) at Weeks 52 AND 76 will be automatically discontinued from the study at Week 76, unless they have a  $\geq 2$ -point improvement from baseline in ClinRO Measure for Eyebrow or Eyelash Hair Loss. See Protocol for more details.
- g Responders who experience a loss of treatment benefit after Week 52 ( $> 20$ -point absolute worsening in SALT score) who were randomized to placebo at Week 52 (randomized withdrawal) will be retreated with their baricitinib dose, as randomized at Baseline (Visit 2). Patients who were randomized to remain on baricitinib (randomized withdrawal) will continue to receive the same dose of baricitinib. See Protocol for more details.

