For the F-DBL safety data will be analyzed on extended safety analysis which includes patients who were continuously treated with baricitinib 2-mg or 4-mg or placebo from baseline and censored in case of dose change. In addition to the above treatment groups, “ALL BARI” will also be included to the summary which includes patients who received at least one dose (2-mg, or 4-mg) of baricitinib at any timepoint during the treatment period.

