the analysis period is defined as first dose date up to min(last dose date, Week 36 visit date, study disposition date). The Week 36 visit date will be imputed if it's missing.

For the long-term safety analysis at the Week 104 DBL, the analysis period defined for the Randomized Withdrawal population is between Week 52 and 104. The analysis period for the retreated population is between the retreatment visit and throughout the min (last dose date+30 days, Week 104 DBL cut-off date).

For the safety analysis at the F-DBL, the analysis period will be Week 0 to 200/248 and will be analyzed based on the safety population. Additionally, exposure data will also be analyzed using randomized withdrawal population and uptitration population.

For selected safety assessments other than events, descriptive statistics may be presented for the last measure observed during post-treatment follow-up (up to 30 days after the last dose of treatment, regardless of study period).

Refer to the compound level safety standards for more details.

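### Final-lock adverse event tables show crude percentages side by side over structurally unequal follow-up, and the SAP states no exposure-adjusted rate

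*SAP*

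**What the plan says.** **Window.** Under SAP 4.14, at the final lock "the analysis period will be Week 0 to 200/248 and will be analyzed based on the safety population".

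**Columns.** Under SAP 4.14.2 the extended safety analysis takes "patients who were continuously treated with Baricitinib 2-mg, or 4-mg and Placebo from baseline and censored in case of dose change", or at permanent drug discontinuation if that comes first. Section 4.2.2 gives the same dose-change rule. An ALL BARI column is added for "patients who received at least one dose (2-mg, or 4-mg) of BARICITINIB at any time of the treatment period". No censoring at dose change is stated for that column.

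**Measure.** As a general rule, 4.14.2 gives the safety population size, the "frequency of patients experiencing the event (n), and the relative frequency", that is n/N × 100. The overview table (deaths, SAEs, discontinuations) and the TEAE and SAE tables use number and percentage. The common-TEAE rule in 4.14.2.1 is a 2% cut-off on the same percentage.

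**Patient-years.** Section 4.14.1 says: "Total patient-years (PY) of exposure will be reported for each treatment group for overall duration of exposure". No section of the SAP divides events by patient-years or plans a time-to-event summary for adverse events.

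**Switching.** The rules are in the footnotes to Figure JAHO.3.2 (3.1.2).
- The placebo rule begins "At Week 36 patients in the placebo treatment arm who have NOT achieved SALT" ≤20, and moves these patients to baricitinib. Placebo responders stay on placebo.
- All baricitinib patients continue past Week 36.
- At Week 52, 2-mg nonresponders go to 4-mg. 4-mg nonresponders without eyebrow or eyelash improvement go to placebo.
- Eligible responders are randomized 3:1 to stay on their dose or switch to placebo.

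**The concern.** A crude percentage rises with the time each patient is observed. Here the difference in time comes from the design rather than from chance dropout. Most placebo patients leave their column at Week 36, whereas baricitinib patients remain until at least Week 52 and some until Week 200 or 248. Differences between columns then mix risk with length of observation, and the shift runs toward more events on baricitinib. The proportional effect is largest for uncommon events that accrue steadily over time.

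**Working it through.** **Plan's own figure.** The safety sections give none. The nearest figure sharing the inputs is the power in SAP 4.1 (more than 90%). With 625 patients allocated 2:2:3 (about 179 placebo, 179 2-mg, 268 4-mg) and response rates of 5%, 20% and 30%, power is 96.0% for 2-mg at alpha 0.01 (96.1% by exact Fisher calculation) and above 99.9% for 4-mg at alpha 0.04. The stated figure is reproduced. The same rates give 268 × 0.30 + 179 × 0.20 ≈ 116 patients eligible for randomized withdrawal. SAP 4.1 expects about 100, which would fit roughly 14% attrition (1 − 100/116).

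**Follow-up by column.** The Week 36 planning rates are applied to the switches, with no dropout, Week 200 as the end, and all baricitinib nonresponders censored at Week 52. Mean follow-up is the sum of share × censoring week.
- Placebo: 0.95 × 36 + 0.05 × 200 = 44.2 weeks.
- 2-mg: 0.20 × 0.75 = 0.15 stay on; 0.15 × 200 + 0.85 × 52 = 74.2 weeks, 1.68 times placebo.
- 4-mg: 0.30 × 0.75 = 0.225 stay on; 0.225 × 200 + 0.775 × 52 = 85.3 weeks, 1.93 times placebo.

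**Expected percentage at equal hazard.** For hazard L per year and 52.18 weeks per year, the expected percentage is 100 × Σ share × (1 − exp(−L × weeks/52.18)). At L = 0.02 the cumulative risks are 1.37% by Week 36, 1.97% by Week 52 and 7.38% by Week 200. Placebo is then 0.95 × 1.37 + 0.05 × 7.38 = 1.67%, and 4-mg is 0.225 × 7.38 + 0.775 × 1.97 = 3.19%. The hazards are assumed, because the documents give none.

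| Hazard per 100 PY (all arms) | Placebo % | 2-mg % | 4-mg % | 2-mg/placebo | 4-mg/placebo |
|---|---|---|---|---|---|
| 2 | 1.67 | 2.78 | 3.19 | 1.67 | 1.91 |
| 5 | 4.09 | 6.75 | 7.69 | 1.65 | 1.88 |
| 20 | 14.92 | 23.39 | 26.05 | 1.57 | 1.75 |
| 100 | 52.24 | 68.30 | 70.90 | 1.31 | 1.36 |

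**Sensitivity of the follow-up ratio to placebo.** With dropout at rate d per year, mean follow-up in years is Σ share × (1 − exp(−d × t))/d, where t is the censoring time in years.

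| Scenario | 2-mg | 4-mg |
|---|---|---|
| Base, d = 0.2 | 1.57 | 1.75 |
| Placebo response 10%, d = 0.2 (lowest) | 1.38 | 1.54 |
| Placebo response 0%, no dropout (highest) | 2.06 | 2.37 |
| End at Week 248, no dropout | 1.75 | 2.06 |
| 10% of 4-mg nonresponders kept on, no dropout | 1.68 | 2.16 |
| Baricitinib response 10%/20%, no dropout | 1.43 | 1.68 |
| Baricitinib response 30%/40%, no dropout | 1.93 | 2.18 |

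The ratio stayed above 1 in every run.

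**ALL BARI.** Counting time on baricitinib, mean follow-up is 75 to 138 weeks (1.7 to 3.1 times placebo), depending on how many switched patients respond later. At 2 per 100 PY this gives 2.8% to 5.1%, against 1.7% on placebo.

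**Check of the alternatives.** Under an equal constant hazard, events per patient-year at risk give a ratio of 1 by construction. A common Week 0 to 36 window gives the same percentage in every arm: 1.4%, 3.4% and 12.9% at 2, 5 and 20 per 100 PY.

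**The case against.** **The method may be defined elsewhere.** The n/N sentence is worded as a general rule, and 4.14, 4.14.1 and 4.14.2 all refer onward to the compound level safety standards. The sections on MACE, VTE, arterial events and malignancy (4.14.5.7 to 4.14.5.10) contain only that reference. A reader might infer that the special-interest events will be shown as crude percentages, or that no rate is planned anywhere. The supplied text supports neither. This objection stands, and it limits the point to what the SAP itself states.

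**The final lock is descriptive.** SAP 4.2.3 plans no inferential tests there, and 4.11.5 notes that the extension periods are not placebo-controlled. A reader might infer a false-positive safety finding, but no test exists to produce one. What remains is a side-by-side display that invites a comparison it cannot support.

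**Exposure is disclosed.** Patient-years per group are reported, so a reader could form a rough rate. This stands only in part. Exposure in 4.14.1 runs from first to last dose and does not stop at the first event. Its default form also excludes time after rescue to baricitinib, which ALL BARI needs.

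**The 2% rule only affects listing.** Longer follow-up can bring an event over the cut-off, as at 2 per 100 PY above, but the result is a longer list. This is accepted, and no weight is placed on it.

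**Rates can mislead in the other direction.** Suppose 10% of each arm has an event, always before Week 36. The percentages are correctly equal. Dividing by the mean follow-up above gives a rate ratio of about 44.2/85.3 = 0.52, so equal early risk would look protective on 4-mg. In addition, follow-up after Week 52 is largely in selected responders, which a rate does not correct. This stands, so replacing percentages with rates is not enough.

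**Conclusion.** The point holds for the SAP as written. The stated measure, applied over Week 0 to 200/248, gives columns whose percentages differ through follow-up alone. The 4-mg column has about 1.9 times the placebo follow-up at planning rates (range about 1.5 to 2.4), and 2-mg about 1.7 times (about 1.4 to 2.1). The resulting 4-mg/placebo ratio of percentages is about 1.9 for rare events and about 1.4 for very common ones.

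These sizes rest on planning response rates, simplified switching and an assumed constant hazard common to all arms. Events concentrated early in treatment would be distorted less. It would go too far to say that equal risk will always appear as excess risk on baricitinib. It would also be wrong to say that every column is censored at treatment change, since that rule is stated only for the three continuously treated groups. Week 0 to 36 tables share one window and are unaffected. The change should be made, but it concerns how long-term safety is displayed and leaves the trial's tests untouched.

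**What to change.** State in SAP 4.14.2 that the final-lock extended-safety and ALL BARI tables of TEAEs, SAEs and discontinuations due to adverse events give, beside n (%), the number of patients with the event per 100 patient-years at risk, with an exact Poisson 95% CI. Do the same for adverse events of special interest if the compound level safety standards do not already require it. If they do, an explicit cross-reference is enough.

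Define time at risk as time to first event. Censor it at dose change for the three continuously treated groups, and count all time from the first baricitinib dose for ALL BARI.

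Add that placebo contrasts rest on the common Week 0 to 36 window, and that neither Week 0 to 200/248 percentages nor rates are interpreted alone as a between-arm comparison. Give the reasons: rates assume a roughly constant hazard, and later follow-up is largely in selected responders.

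The cost is a small extra derivation (at-risk time per event and ALL BARI exposure) and added columns in the tables.

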### 3.1.2. Study Design

[figure not shown]
The study design includes 5 periods: a 5-week screening period; a 36-week double-blind placebo-controlled treatment period; a 68-week long-term extension period; a 96-week bridging extension; and a posttreatment follow-up period. The Schedule of Activities (SOA) will be the same for patients randomized during Stage 1 and Stage 2, except that some patients randomized during Stage 1 might have one or more unscheduled visits after the Decision Point.

- **Period 1:** Screening period (Visit 1) is between 3 and 35 days prior to Visit 2 (Week 0).
- **Period 2:** 36-week double-blind, placebo-controlled treatment period is from Week 0 (Baseline; Visit 2) to Week 36 (Visit 8).
- **Period 3:** 68-week, long-term extension period with randomized withdrawal (for responders) is from Week 36 (Visit 8) to Week 104 (Visit 18).
- **Period 4:** Bridging extension period is from Week 104 (Visit 18) and up to Week 200 (Visit 24)/Week 248 (Visit 26). Subjects who have completed Week 104 and have not

met criteria of permanent discontinuation will have the possibility to remain in the trial for up to 96/144 additional weeks (up to Week 200/248).

- **Period 5:** posttreatment follow-up period; the posttreatment follow-up visit should occur approximately 4 weeks after the last dose of investigational product (IP). Patients who have completed Week 200/248 and who will continue on marketed product beyond Week 200 do not need to complete Period 5 (Visit 801).

Note: Patients who have discontinued IP and remain in the study for more than 28 day without IP will have an Early Termination Visit (ETV); however, a separate follow-up visit (V801) is not required. [Figure JAHO.3.2](#) illustrates the study design. The full visit schedule is outlined in the protocol.

Abbreviations: ClinRO = clinician-reported outcome; EC = exclusion criterion; eGFR = estimated glomerular filtration rate; ET = early termination; IP = investigational product; PBO = placebo; PTFU = posttreatment follow-up; QD = once daily administration; RW = randomized withdrawal 1; SALT = Severity of Alopecia Tool; V = Visit.

Note: Subjects who have completed Week 104 in the Long-term extension and have not met criteria of permanent discontinuation will have the possibility to remain in the trial for up to 96/144 additional weeks (up to Week 200/248) and have similar follow-up procedures.

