### 4.14. Safety Analyses

The general methods used to summarize safety data, including the definition of baseline value are described in Section 4.2.

Safety analyses for Phase 2 and 3 portions will include data from first dose of the study treatment including follow-up data, unless otherwise stated. Patients will be analyzed according to the investigational product to which they were randomized at Week 0 (Visit 2), unless otherwise stated. Safety analyses will take place using the safety population defined in Section 4.2.1.

Safety topics that will be addressed include the following for the Phase 3 portion: AEs, clinical laboratory evaluations, vital signs and physical characteristics, Columbia Suicide Severity Rating Scale (C-SSRS), the Self-Harm Supplement Form, safety in special groups and circumstances, including adverse events of special interest (AESI) (see Section 4.14.5), and investigational product interruptions.

Unless otherwise specified, by-visit summaries will include planned on-treatment visits. For tables that summarize events (such as AEs, categorical lab abnormalities, shift to maximum value), post-last dose follow-up data will be included. Follow-up data is defined as all data occurring up to 30 days (planned maximum follow-up time) after last dose of treatment, where applicable.

For the interim lock(s), all safety data from ongoing patients at time of the interim lock will be included in the safety analysis censored at treatment change (including rescue to a higher dose), unless otherwise stated. Safety data from patients who permanently discontinued the study treatment prior to an interim lock will be included in the interim lock safety analysis up to 30 days post-last dose, censored at treatment change, unless otherwise stated.

For the Phase 3 Weeks 0 to 36 tables, figures, and listings (TFLs) summarizing events in a non-visit-specific manner, including:

- AEs
- C-SSRS
- Shift in laboratory testing
- Treatment-emergent abnormal laboratory testing
- Treatment-emergent abnormal vital signs

the analysis period is defined as first dose date up to min(last dose date+30, Week 36 visit date, study disposition date).

For the Phase 3 Weeks 0 to 36 TFLs summarizing the safety data in a by-visit manner, including

- Observed and change in laboratory testing at scheduled visit
- Observed and change in vital signs at scheduled visit,

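### The final-lock Extended Safety Analysis stops counting events at permanent drug discontinuation, which conflicts with the SAP's own 30-day off-drug window and with its other final-lock rules

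*SAP*

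**What the plan says.** The SAP states the end of the safety window for the final lock in several places.

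- SAP 4.14.2, Extended Safety Analysis: the continuously treated 2-mg, 4-mg and placebo patients are "censored in case of dose change, or after the permanent study drug discontinuation, whichever occurred earlier".
- SAP 4.2.2, the same analysis at the same lock: patients "continuously treated with baricitinib 2-mg or 4-mg or placebo from baseline and censored in case of dose change". Stopping the drug is not mentioned.
- SAP 4.14.2, definition of a treatment-emergent event: "The analysis period is defined as the treatment period plus up to 30 days off-drug including follow-up time".
- SAP 4.14, tables that summarise events: "post-last dose follow-up data will be included". It adds: "Follow-up data is defined as all data occurring up to 30 days (planned maximum follow-up time) after last dose of treatment, where applicable".
- SAP 4.14, interim locks: data from patients who stopped the drug permanently "will be included in the interim lock safety analysis up to 30 days post-last dose, censored at treatment change".
- SAP 4.14, final lock: the period is Week 0 to 200/248, with no post-dose days named.

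SAP 4.14.3 and 4.14.4 also use treatment plus up to 30 days for categorical laboratory and vital-sign summaries. The ALL BARI column, described in 4.2.2 and 4.14.2, has no end rule.

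**The concern.** Two programmers, one working from 4.2.2 and the other from 4.14.2, would produce different adverse event tables for the same lock. If the 4.14.2 sentence is followed, an event that starts ten days after a patient permanently stops 4 mg is missing from the 4-mg column. A treatment-emergent laboratory abnormality in that patient on the same day would count under 4.14.3.

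The effect runs in one direction. SAP 4.14.2 reports events as n/N with N the safety population, so the cut can lower n but leaves N unchanged. The same patient would have been handled differently at an interim lock, where the 30 days are kept. Final-lock counts would then not be comparable with earlier ones for a reason unrelated to the drug.

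**Working it through.** **Step 1: the rules side by side.** No figure in the SAP depends on the cut-off, so there is none to reproduce. The check is a reconciliation of text, followed by day counts.

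| Place | End of window for a patient who permanently stops without a dose change | Off-drug days kept |
|---|---|---|
| SAP 4.14.2, Extended Safety Analysis | discontinuation | 0 |
| SAP 4.2.2, same analysis | not cut by discontinuation | not limited there |
| SAP 4.14.2, treatment-emergent definition | treatment + up to 30 days | up to 30 |
| SAP 4.14, event tables | last dose + up to 30 days | up to 30 |
| SAP 4.14, interim locks | last dose + up to 30 days | up to 30 |
| SAP 4.14, final lock | Week 0 to 200/248 | none named |

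The first row is the only one that expressly removes the off-drug days of a patient who discontinues. The last row leaves completers unclear.

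**Step 2: position of the follow-up visit.** The notes to the study design figure in SAP 3.1.2 put Visit 801 about 28 days after last dose. Since 28 ≤ 30, its nominal date lies inside the 30-day window and outside the cut for a patient who discontinued.

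**Step 3: share of one patient's event window removed.** With D = days on drug = 7 × stop week, and assuming all 30 off-drug days would have been observed, the share is 30/(D + 30). The stop weeks are illustrative.

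| Stop week | D | 30/(D + 30) | Share |
|---|---|---|---|
| 4 | 28 | 30/58 | 51.7% |
| 12 | 84 | 30/114 | 26.3% |
| 36 | 252 | 30/282 | 10.6% |
| 52 | 364 | 30/394 | 7.6% |
| 104 | 728 | 30/758 | 4.0% |
| 200 | 1400 | 30/1430 | 2.1% |

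The share is largest for early stoppers.

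**Step 4: can a study total be given?** It would need the number who stop permanently before any dose change, and an off-drug event rate. The documents give neither. The approximately 625 Phase 3 patients are not a usable base, because the design moves many out of these columns at Weeks 36 and 52 (SAP 3.1.2). As a rough illustration, take the 2:2:3 allocation (179, 179 and 268), the planning response rates in SAP 4.1 (5%, 20% and 30% for placebo, 2 mg and 4 mg), and the 3:1 withdrawal randomization. Assume that the rates still hold at Week 52 and that nobody stops earlier. Those still on their baseline treatment after Week 52 are then 179 × 0.05 + 179 × 0.20 × 0.75 + 268 × 0.30 × 0.75 = 9.0 + 26.9 + 60.3, about 96. Patients on 4 mg who avoid the Week 52 switch through eyebrow or eyelash improvement would add to this. Patients who stop before any switch are also affected, in a number not given.

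**The case against.** The best defence is that SAP 4.14 includes follow-up data only where nothing else is stated, so 4.14.2 may be a deliberate exception. Its wording is also *after* discontinuation rather than at last dose, and could be read together with the 30-day period in the same section. Detail is deferred to compound level safety standards that are not among the documents and may settle the matter. This lowers the certainty about what will be programmed. It does not remove the conflict: 4.14.2 declares no exception, 4.2.2 does not match it, and taking the earlier of two dates most naturally means the dates of the two events themselves.

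The consequences are also limited, and this stands. SAP 4.14.2.2 lists all serious events individually and lists deaths whenever they occurred in the study. SAP 4.14.2.3 summarises events leading to permanent discontinuation. SAP 4.2.3 makes the final lock descriptive. Serious events leave the dose columns but remain in the listings.

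Three stronger readings are tempting, and the documents do not support them.

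- A reader might infer that everything found at Visit 801 is lost. Events that began before the drug was stopped remain. SAP 4.7 separates completing treatment from discontinuing it, so completers are not clearly cut by 4.14.2. Discontinuers who stay in the study more than 28 days off drug need no Visit 801.
- A reader might multiply 30 days by an assumed share of all Phase 3 patients to obtain patient-years or serious events lost. Step 4 shows why that base is wrong.
- A reader might want ALL BARI to follow the dose columns exactly. That column takes in anyone given baricitinib at any time. A dose-change cut would end a rescued placebo patient's follow-up just as baricitinib starts, which defeats the column's purpose.

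**Conclusion.** The SAP gives conflicting end points for the final-lock safety summaries and does not say which governs. Under the literal rule in 4.14.2, events with onset 1 to 30 days after permanent discontinuation, in patients with no earlier dose change, are not counted in the 2-mg, 4-mg and placebo columns. For one such patient the loss is between about half the event window (stop at Week 4) and about 2% (stop at Week 200). This takes the cut to fall at last dose and all 30 days to be otherwise observable. The number of events lost is unknown. It is worth correcting before the tables are produced, because the rule as stated under-counts events in those columns. It does not affect the primary efficacy analysis or any test.

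**What to change.** In SAP 4.14.2 and 4.2.2, use one sentence for event summaries: follow-up in the 2-mg, 4-mg and placebo columns ends at the earlier of dose change and, where the drug was stopped permanently, last dose + 30 days.

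In the final-lock paragraph of SAP 4.14, add that completers also keep the follow-up window of up to 30 days after last dose for event summaries.

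For ALL BARI, state that follow-up ends at last baricitinib dose + 30 days and is not cut at dose change.

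The cost is a few sentences and a change to the censoring date in the programs. The data are already collected. The downside is that event counts may be slightly higher. If the lock has passed, the clinical study report should record which rule was used.
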